#### 2. Intervention:

# Amped-PD: Remote Walking Program Description

(prescribed walking program of 15 hours total over six weeks + concurrent use of SAM device 4 days during early training)

**Overview:** The remote walking program is a self-directed, structured walking program held in home/community settings using the music-based device. Participants will be instructed to complete five home/community-based walking sessions per week (one session/ day, 30 minutes in duration) for six weeks. Participants may choose to perform these 5 training sessions on any days of the week according to their needs.

**Description of Walking Program:** Using the music-based device, participants will conduct the walking sessions at their self-selected pace in

a home/community environment that limits the amount of stops and/or pivot turns in order to optimize continuous walking. For the purposes of this study, home/community environment is considered any environment outside a professional healthcare facility. This includes but is not limited to the home, apartment building, independent living retirement homes, outdoor environments (tracks, parks, sidewalks), office environments and community/ recreation centers.

**Duration of Walking Session:** Each individual walking session will be completed within a 30- minute timespan (i.e., should not be split up throughout the day). Participants are allowed to rest as needed during the 30-minute training period. The time clock will continue to run down continuously once the 30 minutes are started (i.e., if a participant rests for 5 minutes, this will equate to 25 minutes of walking). Participants will be instructed to terminate any walking session in the event of technical or medical issues to allow for adequate resolution.

**Walking program diary:** Participants will be asked to record in a study diary their schedule (dates and times) of walking, location, record of any falls they experience and any comments/issues they experience while using the device (see Appendix VII: Outcome Measures).

Safety Considerations: Participants will be informed of the potential risk of falls that can occur as part of the walking program in the community. Determination of a safe environment (as described in the Music-Based Device Training section above) will be discussed with the participant to mitigate external risk factors that could lead to a fall. Participants will be instructed to reach out to their healthcare provider if experiencing dizziness, chest pain, or other serious symptoms and will be asked to notify the study team following the episode. If participants experience a fall while using the device, they are advised to seek medical attention (if needed) and record the incident in their study diary. In addition, participants will be asked to contact the research team following the event to determine whether it is safe for them to continue. The physical therapist will examine the context of the fall. It is possible to discontinue the training program due to but not limited to the following reasons: (1) participant self-report of injuries that prevent them from participating fully and safely in the program; (2) participant selfreports on change in function and mobility after a fall; (3) concerns related to the execution of the walking program or proper use of the device, its components, and functionality; (4) considerations related to a change in participant's walking function.

The program may be continued based on discretion of the physical therapist if the fall is determined to be ancillary, unrelated to the training program or the device, resulted in negligible or insignificant injuries postfall, and no change in safety determination. Participants will be contacted by a member of the study team weekly to see if they have any questions or concerns with the walking program. However, participants will be encouraged to reach out to the research team at any point if they do not feel comfortable using the device.

Physical therapy check-in call: During the baseline evaluation visit, the research team will ask the participant which time each week is preferred to have a check-in call. This phone call will last approximately 5-10 minutes to check on participant engagement in the walking program, and to provide guidance regarding any questions/concerns and/or any medical/ technical issues. If participants are unable to carry out the walking program 5- days per week, a study staff member will discuss the barriers to implementation (by phone) and suggest ways to optimize adherence to the program (e.g., setting a schedule). A study staff member will also inquire about adverse events during the weekly phone call and ensure that the participant is comfortable with the walking program.

Step Activity Monitoring: After completing 4 days of wear prior to starting training, the participant will continue to wear the SAM for an additional 7 days upon intervention initiation (total of 11 days continuous wear). During training, both the SAM and the shoe sensors of the music-based device can be worn simultaneously on the same side of the body without interfering with a participant's walking and/or increasing the risk for trips/falls. Participants will return the SAM to study personnel via a pre-labeled, addressed envelope to mail following 11 days of continuous monitoring period. The researchers will download the data and will store in a secure server.

Interruptions in training: In the event of unavoidable interruptions in training, booster sessions may be implemented to promote treatment fidelity. For training interruptions that last up to 2 weeks, the participant will continue the program and receive booster sessions at 100% of the time missed. For training interruptions of greater than 2 weeks, the training will be restarted after a reasonable washout interval, as determined by the Principal Investigator (a licensed physical therapist). If training interruption resulted in permanent change in eligibility, the participant will be withdrawn from the study.

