# **Study Procedures**

# **Primary Screen (approximately 10 minutes):**

A primary screen will be conducted over the phone to make a preliminary determination if potential participants meet the initial inclusion / exclusion criteria prior to scheduling a more in-depth, in-person screening assessment. During the phone screen (see Appendix I: Primary Screen), potential participants will be asked their age (exclude if < 40 years of age), if they are currently participating in physical therapy (exclude if yes), if they are currently performing walking exercise of at least 30 min for > 3x/week (exclude if yes), and if a medical doctor diagnosed them with Parkinson disease (exclude if no). Potential participants will be asked about their ability to walk independently without physical assistance or an assistive device (exclude if no), their history of falls of > 1 fall over the past 3 months, or a singular fall over the past 3 months that is PD-related, with a fall defined as an unexpected event that caused a person to unintentionally land on a lower surface (e.g. floor, ground), regardless of presence or absence of resultant injury (exclude if yes), and whether they experience freezing episodes during daily walking (exclude if moderately or significantly disturbing – see operational definition under exclusion criteria). Lastly, a brief medical history based on self-reports from the participant will be reviewed to determine the following:

- Those with known cardiac problems that interfere with the ability to safely exercise (e.g., congestive heart failure, uncontrolled cardiac arrhythmias, chest pain) will be excluded.
- Those with known orthopedic conditions in the lower extremities or spine that may limit walking distance (e.g., severe arthritis, spinal stenosis, significant pain) will be excluded.
- Those with other medical conditions that would preclude successful participation, as determined by a physical therapist on the research team, will be excluded. The physical therapist will make this determination based on participant self-report and a PTs informed questioning which is part of a licensed PTs training.

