# Active-Control Intervention: Remote Walking Program Description

(Prescribed walking program of 15 hours total over six weeks + concurrent use of SAM device 4 days during early training)

**Overview:** The Active-Control Intervention is similarly structured as Amped-PD Intervention, with the only exception of not using RAS/ music-based device. Participants will be instructed to complete five home/community-based walking sessions per week (one session/ day, 30 minutes in duration) for six weeks.

**Description of Walking Sessions:** Without using the music-based device, participants will conduct the walking sessions at their self-selected pace in a home/community environment. All other considerations as outlined above apply to this intervention.

**Duration of Walking Session:** Each individual walking session will be completed within a 30- minute timespan (i.e., should not be split up throughout the day. Participants will be asked to use their own wristwatch,

timer, or cellphone to monitor the time/ duration of walking session. Participants are allowed to rest as needed during the 30-minute training period.

**Walking program diary:** Participants will be asked to record in a study diary their schedule (dates and times) of walking, location, record of any falls they experience and any comments/issues they experience while performing the walking program.

**Safety Considerations:** Same as above as outlined in Amped-PD. **Physical therapy check-in call:** Same as above as outlined in Amped-PD. **Step Activity Monitoring:** Same as above as outlined in Amped-PD.

Interruptions in training: In the event of unavoidable interruptions in training, booster sessions may be implemented to promote treatment fidelity. For training interruptions that last up to 2 weeks, the participant will continue the program and receive booster sessions at 100% of the time missed. For training interruptions of greater than 2 weeks, the training will be restarted after a reasonable washout interval, as determined by the Principal Investigator (a licensed physical therapist). If training interruption resulted in permanent change in eligibility, the participant will be withdrawn from the study.

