# 3. Second Evaluation Visit: Post-Assessment Visit (approximately 2-3 hours):

The post-intervention assessment visit will be scheduled within approximately 7 days of completion of the structured walking program and take place at the Center for Neurorehabilitation at Boston University. This visit will entail the same battery of assessments performed at Baseline Assessment including: 10MWT, 6MWT, Borg's RPE, Mini BESTest, MDS-UPDRS I/II/III, 5xSTS, PDQ-39, SRHI, GDS. Quantification of movement will be performed using wearable sensors to measure balance and walking as examined in the aforementioned battery of assessments.

Further, a usability questionnaire will be administered for those who completed Amped-PD. For both Amped-PD and Active-Control groups, participants will be asked to bring in their study diary for study personnel to review and to make a copy for their data file. This study diary will be returned to the participant for continued use if needed during the Follow-up Period. For the Amped-PD group, they will have continued access to the music-based device during the Follow-up Period. The SAM monitor will be given to the participant to wear for 7 days during Follow-Up Training. Participants who withdraw or are withdrawn prior to completing their last walking session may be asked to complete closing visit activities, if feasible.

4. Follow-Up Walking Program (2 weeks): Extended Remote Walking Program

Description for both groups (recommended continuation of routine walking + concurrent use of SAM device 4 days during follow-up training)

**Overview:** Participants in both Amped-PD and Active-Control groups will be recommended to carry out the walking program independently for another 2 weeks,

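### During the 6-week program, prompt contact with the team is requested only after a fall during device use, so a fall outside a walking session may wait for the weekly call

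*Protocol*

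**What the plan says.** The fall procedure is in the Protocol, section 2 (Intervention), under Amped-PD, in the Safety Considerations paragraph. It opens with a condition: "If participants experience a fall while using the device, they are advised to seek medical attention (if needed"). After asking for a diary entry, it adds that "participants will be asked to contact the research team following the event to determine whether it is safe for them to continue". The therapist then looks into the circumstances of the fall and decides whether training stops or goes on. The listed reasons for stopping are expressly not exhaustive.

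Active-Control walks without the device. Its Safety Considerations and check-in call entries each read "Same as above as outlined in Amped-PD", and its description of the walking sessions says "All other considerations as outlined above apply to this intervention".

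Three other parts of the Protocol bear on falls:

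- **Check-in call:** "A study staff member will also inquire about adverse events during the weekly phone call". This applies in both arms.
- **Diary:** participants in both arms record any falls. At the Post-Assessment visit they are "asked to bring in their study diary for study personnel to review".
- **Primary Screen:** people with more than one fall in the past 3 months are excluded, "or a singular fall over the past 3 months that is PD-related". The accompanying definition counts a fall "regardless of presence or absence of resultant injury (exclude if yes").

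**The concern.** The condition for prompt contact is narrower than the hazard it addresses. Participants have Parkinson disease and walk without supervision for 30 minutes, five times a week. A fall in the kitchen between sessions can signal a change in balance or walking just as a fall during a session can. Yet only the second leads to a request to call before walking again.

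What is at stake is the timing of a safety judgement. A participant who falls between sessions and has no serious symptoms is not asked to call, so the therapist may first consider whether it is safe to continue after several more walks. The four primary outcomes named in the SAP do not include falls, and the point does not depend on the analysis.

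**Working it through.** The plan gives no figure for this delay. The check has two parts: the routes by which a fall could reach the team, and the delay that the slowest reliable route allows.

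**Routes for a fall outside a session, weeks 1 to 6**

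| Route | Where in the Protocol | Reaches such a fall? | Prompt? |
|---|---|---|---|
| Fall instruction (contact, then therapist review) | Amped-PD, Safety Considerations | Not as worded; conditional on device use | Yes, where it applies |
| Symptom instruction | Same paragraph | Only with dizziness, chest pain or other serious symptoms | Yes |
| Ending a session for medical issues | Amped-PD, Duration of Walking Session | No; concerns events in a session | – |
| General invitation to call | Section 1.d; Safety Considerations | Possibly; covers questions, concerns and discomfort with the device, and does not name falls | Only if the participant takes the initiative |
| Weekly call | Physical therapy check-in call; carried to Active-Control | Yes, if reported as an adverse event | Up to a week later |
| Diary | Both arms; review at Post-Assessment | Yes | No; the visible text has it reviewed after the 6 weeks |

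The contact request refers to the event just described, and the review refers to the fall just described. Neither has a condition of its own. The reasons for stopping are not tied to device use, but the therapist can apply them only once the team knows of the fall.

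**Active-Control.** Read literally, the device-use condition can never be met there. The cross-reference clearly means the safety text to apply, so the sensible reading is that falls during a control session are covered. What remains is wording that was not adapted. The control diary entry was adapted: its clause on comments and issues refers to performing the walking program, where the Amped-PD entry refers to using the device.

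**Delay if the weekly call is the first report**

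Inputs: one call per week (check-in call); five sessions per week, one per day, 30 minutes each, on days the participant chooses (Amped-PD Overview).

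- Longest wait: one call interval = 7 days.
- Mean wait, with falls equally likely on any day: 7 / 2 = 3.5 days.
- Sessions in 7 days at the prescribed rate: 5, or 5 × 0.5 h = 2.5 h.
- Mean sessions before the call: 5 / 2 = 2.5, or 2.5 × 0.5 h = 1.25 h.
- Upper limit on sessions: five is not the maximum, because days are free. With sessions on days 3–7 of one program week and days 1–5 of the next, the 7 days from day 4 to day 3 hold 4 + 3 = 7 sessions, or 7 × 0.5 h = 3.5 h.

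**The case against.** The strongest reply is that the arrangement is reasonable: immediate self-report for falls during the study activity, and a weekly inquiry for everything else, in people screened as independent walkers who need no guarding. Much of this stands. It is why the point is minor, and why the gap concerns promptness rather than detection.

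A reader might infer that a fall outside a session never reaches the team or the therapist. The documents do not support that, given the weekly inquiry and the diary of any falls in both arms. A reader might also infer that falls during control-arm sessions are left out. The cross-references tell against that.

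The Safety Considerations paragraph also lets training continue after a fall judged unrelated to the program or the device, and lists altered function following a fall, without qualification, as a reason to stop. This may show that a wider review was intended. It is not conclusive, since an unrelated fall can also happen during a session, and it concerns the decision after review, not what prompts contact. If wider cover was intended, the edit only makes it explicit.

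The comparison with the Primary Screen has limited force. That is an entry criterion and not an on-study stopping rule, and a single fall unrelated to PD does not exclude. It shows that the plan regards falls in any setting as relevant to suitability. It does not show that a fall during training should end participation.

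Finally, the diary form, consent form and other appendices were not available. They may contain fall or adverse-event instructions, so the point is limited to the visible text.

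**Conclusion.** The point holds as a low-severity, cheap safety improvement. In the visible text for the 6-week program, prompt contact followed by therapist review is requested only for a fall during device use. For a fall outside a session, the team may first hear at the weekly call, up to about 7 days and about 5 sessions later, with 7 sessions possible in an unfavourable week.

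These figures assume that the participant does not call unprompted, does all prescribed sessions and reports the fall when asked. The means also assume that falls are spread evenly over the week. The figures describe delay only. The documents give no fall rate, and eligibility screening lowers the risk, so the number of participants affected cannot be stated.

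A reader might go further and infer uneven safety ascertainment between arms or bias in the results. The documents do not support this: the diary and the weekly inquiry apply to both arms, and no link to an outcome is shown. Nothing is claimed about the 2-week follow-up, whose text is incomplete.

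**What to change.** In the Safety Considerations paragraph, replace the device-use condition with: *any fall during the training program, in either arm, during or outside a walking session*. Apply the fall definition already given in the Primary Screen. The existing cross-reference then carries the change to Active-Control and removes the wording that does not fit that arm. Add a line to the diary instructions asking whether the fall happened during a session and whether the device was in use, so that device-related falls can still be identified.

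The cost is one phrase, one diary line, and a few more calls and brief therapist reviews for minor falls. Eligibility, visits, outcomes and analysis are unchanged. If an appendix already contains this instruction, the paragraph need only be brought into line with it.

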# **Study Protocol**

# **Study Design:**

The study is a parallel community-based 2-arm randomized controlled trial (RCT) in which the study evaluations will take place at the Center of Neurorehabilitation (CNR) at Sargent College, Boston University. We will enroll 44 community-dwelling adults ages 40-80 yrs with idiopathic PD of mild to moderate disease severity, who are independent community ambulators. We will exclude those with atypical PD, have significant freezing of gait, have history of falls in the past 3 months, have a comfortable walking speed <0.4 m/s, and significant cognitive or hearing impairments. Eligible participants will be randomly allocated to either

[figure not shown]

Figure 1 Study flow. Abbreviations: CoV: Coefficient of Variation; SAM: Step Activity Monitor; SRHI: Self-Report of Habit Index

Amped-PD (experimental arm) or Active Control (control arm). Assessments will include a standard set of motor and non- motor assessments and will be administered at Baseline, Post-Assessment (after 6 weeks of training), and Follow-up (after 2 additional weeks of unstructured training). Figure 1 summarizes the study flow for the protocol.

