- 6. Based on clinical expertise and judgement, the physical therapist conducting the in- person screening will determine if a participant requires additional guarding and/or assistance during walking activities (i.e., occasional hand contact to maintain balance or dynamic stability and/or an assistive device). If guarding is needed at any point during the evaluation,

the participant will be excluded.

- **1.b Baseline Assessment:** Participants who are deemed eligible through the inperson screen will continue on to complete the remainder of the baseline assessment measures, including:
  - Demographic questionnaire consisting of age, gender, education level, living situation, employment, ethnicity, race, and PD-specific questions. This form will be completed interview-style by the physical therapist.
  - Medication form pertaining to PD and non-PD medications (see Appendix VII: Outcome Measures). Participants will be asked during the phone screen to bring their medication list to this first evaluation visit. The physical therapist will transcribe the medications onto the designated form. Medication lists that contain identifiable information will be given back to the participant and not be kept by the research team.
  - Motor & Functional Measures:
  - Dynamic balance will be measured using the Mini Balance Evaluation Systems Test (Mini BESTest). This test comprises of 14 items that span anticipatory postural adjustments, reactive postural control, sensory orientation, and dynamic gait.
  - ii. Motor symptoms will be assessed using the Movement Disorder Society Unified Parkinson Disease Rating Scale (MDS-UPDRS)-III (see Appendix VII: Outcome Measures). The MDS UPDRS is the most widely used clinical rating scale fork Parkinson disease. Part III is a motor examination (33 scores summed from 18 questions) conducted by the rater. Total scores can range from 0 to 141, with higher scores indicating worse disease severity.

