- 1.cRandomization: At the completion of procedures for Baseline Assessment, the participant will be randomized to receive either the experimental or control arm of the intervention. The experimental arm, called Amped-PD, is a 6-week community-based structured walking program that uses a music-adaptive RAS followed by 2 weeks of unstructured walking protocol (continue as desired) for a total of 8 weeks. The control arm, called Active-Control is a similarly structured 6-week community-based walking program that does not use RAS, followed by 2 weeks of unstructured walking protocol (continue as desired) for a total of 8 weeks of training. Block randomization with balanced allocation between the two groups will be implemented. A randomization list will be generated prior to enrollment of participants. The researcher will gain knowledge of treatment assignment only after procedures in In- person Screen and Baseline Assessments have been completed.

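### Participants withdrawn after a lasting loss of eligibility can lose their week-6 and week-8 primary outcomes; stopping training should be separated from leaving the study

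*Protocol*

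**What the plan says.** Two rules deal with a participant who can no longer train.

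- **Safety Considerations (Protocol, section 2, Amped-PD).** After a fall, "It is possible to discontinue the training program due to but not limited to the following reasons". The listed grounds include injury, self-reported change in function, and "considerations related to a change in participant's walking function". Leaving the study is not mentioned. The Active-Control section carries this over: "Same as above as outlined in Amped-PD".
- **Interruptions in training (Protocol, section 2, both arms, same wording).** Interruptions of up to 2 weeks are made up with booster sessions, and longer ones lead to a restart. The paragraph then ends: "If training interruption resulted in permanent change in eligibility, the participant will be withdrawn from the study".

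On data from people who leave, section 3 (Second Evaluation Visit) says: "Participants who withdraw or are withdrawn prior to completing their last walking session may be asked to complete closing visit activities, if feasible". It gives no content or date for that closing visit and assigns no step-monitor wear to it.

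The SAP names four primary outcomes: moderate-intensity minutes, daily steps, stride time variability and habit strength. It compares arms on change from baseline at 6 and 8 weeks. It names no analysis population and no method for missing outcomes.

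**The concern.** The interruption rule ends study participation, not just training. A participant without a 6- or 8-week value has no change score and drops out of the comparison by default.

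That loss is unlikely to be random. Eligibility rests partly on walking ability: section 1.a says "If guarding is needed at any point during the evaluation", the person is excluded, and it also requires independent walking for at least 10 minutes. Someone who permanently ceases to meet such criteria has probably worsened in walking, and three of the four primary outcomes are walking measures.

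Two things are at stake. The within-arm change over time, which the SAP also tests, may look better than it was. The between-arm contrast may be biased if the arms lose different numbers of people, or people who differ in how much they worsened.

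**Working it through.** **1. The passages side by side.** Take a fall that leaves a lasting loss of walking function. Under Safety Considerations, training may stop. If the interruption also makes the person permanently ineligible, the interruption rule removes them from the study. Both rules can apply, and the text does not say which governs. Section 3 then permits a closing visit but does not require one. A closing visit held in week 3, say, would not supply a 6-week value, and nothing secures a week-8 value. Step-monitor wear is tied to attending the visits in sections 3 and 4, so daily steps and moderate-intensity minutes have no stated collection route for withdrawn participants.

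**2. The plan's own figure.** The protocol states "We will enroll 44 community-dwelling adults ages 40-80 yrs with idiopathic PD" and "Block randomization with balanced allocation between the two groups will be implemented", hence 44 / 2 = 22 per arm. The 44 cannot be reproduced, because no effect size, SD, power or dropout rate is given. For orientation only, two-sided 0.05 and 80% power with a standardised difference of 0.85 give 2 × (1.960 + 0.842)² / 0.85² = 21.7, so 22 per arm with no dropout. The 0.85 is not in the documents.

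**3. Within-arm shift (assumed inputs).** Let k be the number lost from an arm of 22, and g the amount, in SDs of the change score, by which their mean change is worse than that of those retained. The mean among those retained exceeds the full-arm mean by (k/22) × g.

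- k = 1, g = 1.0: 1/22 × 1.0 = 0.045 SD
- k = 3, g = 1.5: 3/22 × 1.5 = 0.205 SD

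**4. Against the precision of the trial.** If all the loss is in one arm, the same shift enters the contrast. The standard error of the difference is √(1/22 + 1/22) = 0.302 SD, so the shift is 0.045/0.302 = 0.15 to 0.205/0.302 = 0.68 of a standard error. With the reduced arm of 19, the standard error is √(1/19 + 1/22) = 0.313 and the upper ratio is 0.65.

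**5. Loss in both arms.** With the same g in each arm, the between-arm bias is (k1 − k0)/22 × g. Type I error is by normal approximation, with standard error √(1/(22 − k1) + 1/(22 − k0)). Two-sided 0.05 is assumed, since the SAP states it only for secondary outcomes.

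| Lost (arm 1, arm 0) | g | Between-arm bias (SD) | Type I error |
|---|---|---|---|
| 2, 2 | 1.0 | 0 | 0.050 |
| 3, 1 | 0.5 | 0.045 | 0.052 |
| 3, 1 | 1.0 | 0.091 | 0.060 |
| 3, 1 | 1.5 | 0.136 | 0.072 |
| 4, 0 | 0.5 to 1.5 | 0.091 to 0.273 | 0.059 to 0.138 |

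Swapping the arms reverses the sign of the bias.

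**6. Power.** For the orienting difference of 0.85, power is 80.5% with 22 per arm, 76.7% with 20 and 72.2% with 18.

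**The case against.** The strongest reply is that the rule is narrow and the same in both arms. Most interruptions keep the person in the trial through boosters or a restart; only a permanent change leads to withdrawal. Section 3 does provide for assessing people who have been withdrawn. The closing sentence of the interruption rule does not mention health, and no formal rescreening is described. The entry criteria could not be reapplied literally in any case: screening excludes people already walking for exercise at least 30 minutes more than 3 times a week, while the program prescribes 30 minutes 5 times a week. Finally, section 4 breaks off mid-sentence in the available text, about where the final visit would be described, so some week-8 provisions may simply not be visible.

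Much of this stands, and it rules out several stronger readings.

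- A reader might infer that the two rules contradict each other. They do not. One is a discretionary stop of training after a fall, the other a withdrawal on a narrower trigger. They overlap without being reconciled.
- A reader might infer that everyone who worsens loses the primary outcomes. The boosters, the restart and the optional closing visit make loss possible, not certain.
- A reader might infer that the trial is tilted towards Amped-PD. The rules are symmetric, and equal loss with an equal gap leaves the contrast unbiased. Only Amped-PD raises the tempo, but section 1.d says the 5% step is small, is reversed if not matched, and need not be followed. Equal loss cannot be presumed, but no direction can be inferred.
- A reader might infer that the home-based outcomes need no contact with the clinic. Section 1.b has a physical therapist calibrate the monitor to each participant's gait; only its return by mail is described. Stride time variability is a gait measure, and the gait sensors are worn during in-person walk tests.

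The reply does not supply a required assessment at weeks 6 and 8 for withdrawn participants, or an analysis population.

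**Conclusion.** The point holds as a design weakness that is cheap to remove. As written, the plan can produce avoidable missing primary outcomes that are plausibly related to worsening. Within-arm change may be flattered. The between-arm contrast may be biased in either direction, but only if the number lost, or how much worse they did, differs by arm.

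On the assumed inputs the bias is a fraction of one standard error, not enough by itself to create or erase a large effect. In a trial of 44, though, it rests on only a few participants. Every value of k and g is an assumption, because the documents give no dropout rate and no SD. For habit strength in particular, nothing in the documents supports a specific gap. If all such participants were assessed at both times and analysed as randomised, this source of bias would be zero.

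**What to change.** - **Interruptions in training (both arms).** State that participants who permanently cease to be eligible stop training but stay in the study for outcome assessment unless they withdraw consent. Reconcile this with Safety Considerations. The decision on when training stops remains with the investigators.
- **Section 3.** State that these participants will be asked to complete the week-6 and week-8 assessments on the calendar schedule: the habit index (SRHI, a 12-item self-report) by phone or mail, step-monitor wear where a calibrated monitor can be supplied, and instrumented walk tests only when judged safe.
- **SAP.** State that all available outcomes are analysed in the arm to which the participant was randomised.

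The cost is a few sentences, some calls and mailings, and a possibly more diluted effect estimate. Stride time variability may still be missing for some participants.
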